## The effects of postnatal depression on child development

*Cognitive development*: Postnatal depression has been found to have an adverse influence on general cognitive functioning, both in infancy and through childhood (see reviews by Sohr-Preston and Scaramella 2006 and Murray and Cooper 2003). A number of studies have found that the negative effects are more likely in more disadvantaged populations (Hay and Kumar 1995, Sharp et al 1995, [name] et al 2008, Petersen et al 2001) and some have shown that boys are more at risk (Sharp et al 1995, Milgrom et al 2004). Chronicity of PND has been particularly associated with worse outcomes in several large-scale studies (Sohr-Preson et al 2006, Petterson and Burke-Albers 2001, NICHD Early Child Care Research Network 1999, Brennan et al 2000). In addition to general cognitive ability, specific cognitive skills, notably child attention (Breznitz and Friedman 1988, Hay et al 2001), has been found to be negatively affected by maternal depression. Our own current work, in collaboration with the large-scale Avon Longitudinal Study of Parents and Children (ALSPAC), indicates that PND has an adverse effect on infant attentional persistence, especially if depression becomes chronic.

*Behaviour problems*: Adverse effects of PND on behavioural problems have been found in early childhood as well as at school age and beyond, as indicated by informants both inside and outside the family (Murray and Cooper 2003). For example, a number of studies using independent teacher reports have found converging evidence of poor behavioural outcomes (Alpern and Lyons-Ruth 1993, Essex et al 2001, Sinclair and Murray 1998, Essex et al 2003). As with cognitive functioning, boys may be more at risk (Sinclair and Murray 1998). While some studies have shown that early postnatal depression has independent effects on later child behaviour problems (Wrate et al 1985, Dawson et al 2003), and others have not (Brennan et al 2000, Philipps and O'Hara 1991), there is consistent evidence for adverse

effects if the depression becomes chronic (Petterson and Burke-Albers 2001, NICHD Early Child Care Research Network 1999, Alpern and Lyons-Ruth 1993, Trapolini et al 2007).

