### 6. STUDY DESIGN

#### 6.1 Summary of Study Design

The study is a randomised controlled trial. All participants will receive CBT. Participants will be randomised to a treatment arm, either VFT or PMR. There will be four minimisation criteria for the randomisation: child gender, socioeconomic status, infant negative emotionality, and severity of PND.

Those taking part will receive a baseline assessment, a home visit at which they will be given the opportunity to ask any questions and discuss the study, give informed consent, have baseline measures of them and their infants taken, and be randomised to a treatment arm. They will then receive twelve therapy sessions, all conducted in the home. The first five will be weekly, the next five will be fortnightly, and then the final two will be at 6 and 10 months after the end of the main ten therapy sessions (these latter two will be booster sessions). In addition, assessments will be conducted prior to the start of therapy, at end of the therapy (child age approximately 12 months), and again when the child reaches 24 month in age (approximately one year after the main therapy ends). Participants will receive a total of thirteen therapy and four assessment visits over a period of approximately 18 months. Visits may be divided further according to the convenience of the participants.

	Months postpartum						
	5-6	6-7	8-11	12	16	20	24
Recruitment							
Screening Interview							
Assessment I							
Weekly Therapy Sessions (5)							
Fortnightly Therapy Sessions (6)							
Assessment II							
Booster Therapy Session I							
Booster Therapy Session II							
Assessment III (2)							

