#### 6.4.3 Study Assessments

The research assessors will not be involved in any way with the treatment and will be blind to treatment condition. There will be three primary assessment points: (i) before treatment when the infant is 4½ - 9 months, (ii) at the end of the treatment when the infant is 12 months, and (iii) at follow-up a year later when infant is 24 months. At all three time-points assessments will be made in the family home. Interactions between mother and infant, using toys that we will provide, will be filmed and coded (by coders blind to therapy arm). At 6 months, a full assessment (using the SCID) of the mother's mental state will also take place. At the second assessment visit (child 12 months old) assessment of maternal appraisal of infant facial and vocal expression task, assessment of child attachment tasks ((i)mother/child play, audio clips to child in mother's absence, reunion (ii) assessment of the mother's manner in which she conveys information about different attachment scenarios to her child) will be conducted. In addition the CBCL and language scale of the BSID-III, and the Health Care Utilisation Questionnaire will be conducted. At the third assessment visit (child 24

months) an additional assessment will take place in our research unit to assess the child's cognitive and language development (Bayley BSIDIII), attention (ECVT, Leiter, Spacial Conflict and Visual Search tasks) and emotional regulation (Rothbart Lab-TAB). In addition, the Attachment Q-Sort will be conducted and the Health Care Utilisation Questionnaire will be given to the participant. Mothers will also be asked to complete a questionnaire on their musical training and habits. Mothers who have already completed the final assessment will be sent a copy via post/email (according to their preferred method).

In addition the EPDS will be repeated during the 6th therapy session to monitor maternal mood. Finally, assessments of the partners of mothers in the study will be conducted by questionnaire, in agreement with the mother, and where the partner chooses to opt-in. EPDS and GHQ-12 will be administered at each assessment point to gauge the partner's mental state. A health history questionnaire will also be administered (Partner Additional Questions). The partner's mental state will be analysed as a covariate.

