#### 9.2 Analysis

With regard to child behaviour problems, a sample size of 57 allows for differences between groups of 0.532 standard deviations to be detected at the 5% significance level and 80% power. Trapolini and colleagues (2007) report Child Behaviour CheckList (CBCL) maternal ratings of externalising behaviour in 4-year-olds. These were grouped according to mothers' depression, as never, sometimes and chronic. The standard deviation of the mothers' scores in the chronic depression group was 7.70, which would allow a difference of 4.08 to be detected if similar variability was observed in this trial. The means and standard deviations in our current Trust programme on the 65% of the sample analysed so far, for 2-year-old children of mothers who remain depressed at 6 months, are very similar to those of Trapolini.

For attachment, van Doesum and colleagues (2008) report Attachment Q-Sort (AQS) security in children 18 months of age, with a common standard deviation of 0.326, which would allow for a difference of 0.17 to be detected if similar variability was observed in this trial.

It is hypothesised that, compared to the control treatment, VFT will lead to better cognitive development, fewer behaviour problems, and a higher rate of secure attachment (Hypothesis 1). To test Hypothesis 1 ANOVAs will be conducted (with each of the child outcomes measured at 24 months as the dependent variable and the treatment group as a betweengroup factor). The three secondary outcome variables will be analysed similarly. Hypothesis 2 has three components: (i) to examine whether, compared to the control group, VFT leads to greater improvement in the three parenting capacities, ANCOVAs (co-varying for the 6m baseline measure) will be performed on each capacity; (ii) to test for mediation, initially the role of single mediators will be examined using standard regression analysis (including any relevant covariates) (Kraemer, et al, 2002); (iii) to establish the unique contribution of each mediator (since the potential mediators might be associated), exploratory mediational analysis using bootstrapping techniques will be conducted (in line with Preacher et al 2007), that include the two non-targetted maternal capacities as covariates. Given the increased complexity of the models including covariates, and our sample size, bootstrapping techniques will be used to also provide confidence intervals (after MacKinnon & Fairchild, 2009).

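### The 24-month ANOVAs name treatment group as their only term although allocation is minimised on four factors; if those factors are prognostic, standard errors are somewhat too large and some power is lost

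*Protocol*

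**What the plan says.** Protocol section 6.1 sets the allocation: "There will be four minimisation criteria for the randomisation: child gender, socioeconomic status, infant negative emotionality, and severity of PND".

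Section 9.2 sets the primary analysis as ANOVAs of each child outcome at 24 months, with "the treatment group as a betweengroup factor". It names no covariate for these models and says that the secondary outcomes will be handled in the same way.

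Adjustment does appear elsewhere. For the parenting capacities under Hypothesis 2, section 9.2 specifies "ANCOVAs (co-varying for the 6m baseline measure) will be performed on each capacity", and its mediation regressions allow for relevant covariates. Section 6.4.3 adds "The partner's mental state will be analysed as a covariate", but that is not a minimisation factor and is not tied to the primary ANOVAs.

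The background (section 4, on the effects of postnatal depression on child development) gives some reason to expect prognostic value. On cognition it says "A number of studies have found that the negative effects are more likely in more disadvantaged populations" and "some have shown that boys are more at risk". On behaviour problems it says "As with cognitive functioning, boys may be more at risk".

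**The concern.** Minimisation makes the arms more alike on the balancing factors than simple randomisation would. If those factors predict outcome, the estimated arm difference varies less from trial to trial. A one-way ANOVA does not know this: it leaves the variance due to the factors in the residual and computes its standard error as if allocation had been unrestricted. The intervals are then too wide and the test rejects less often than 5% under the null.

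Every mother in the trial has postnatal depression. A factor that makes the effect of that depression on the child worse should therefore act as a predictor of outcome within the trial. What is at stake is efficiency. Section 9.1 sizes the trial for 80% power with almost no margin, and data already held at randomisation could add to that power.

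**Working it through.** **Inputs.** From section 9.1: SD 10.9, difference 5.8, 5% level, 80% power, 57 per group, 20% loss, 72 per group (144 in all), standardised difference 0.532. Sidedness is not stated; two-sided is assumed. R2, the share of outcome variance explained by the four factors, is not in the protocol and is shown as a range.

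**1. The protocol's own figure.** 5.8/10.9 = 0.532 SD. A two-sided t-test at 80% power needs 56.4 per group, rounded up to 57, and power at 57 is 80.4%. Allowing for loss, 57/0.8 = 71.25, rounded up to 72. The stated sample size reproduces, and it assumes an unadjusted comparison.

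**2. Power with adjustment.** Adjustment reduces the residual SD to SD × √(1 − R2), so the effective standardised difference is 0.532/√(1 − R2). With 57 per group and the t-test:

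| Assumed R2 | Effective difference | Adjusted power | Unadjusted SE relative to adjusted SE, 1/√(1 − R2) |
|---|---|---|---|
| 0 | 0.532 | 80.4% | 1.000 |
| 0.05 | 0.546 | 82.4% | 1.026 |
| 0.10 | 0.561 | 84.3% | 1.054 |
| 0.20 | 0.595 | 88.3% | 1.118 |

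The last column compares the two models' standard errors. It equals the excess of the unadjusted SE over the true sampling variability only if balance is perfect, which neither minimisation with a random element nor 20% loss delivers. Step 3 therefore simulates the allocation.

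**3. Simulation.** 144 mothers were minimised on four binary factors with assignment probability 0.8 (assumed; the protocol gives no value), 20% were lost at random, and 3,000 replicates were run. The Monte Carlo standard error of a 5% rejection rate is √(0.05 × 0.95/3000), about 0.4 percentage points.

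| Assumed R2 | Size, ANOVA | Size, adjusted | Power, ANOVA | Power, adjusted |
|---|---|---|---|---|
| 0 | 5.7% | 5.6% | 81.4% | 81.1% |
| 0.10 | 4.4% | 5.4% | 82.2% | 85.4% |
| 0.20 | 3.2% | 4.6% | 82.4% | 88.2% |

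At R2 = 0.20 the mean ANOVA SE was about 0.186 against a true sampling SD of about 0.171, and 0.186/0.171 = 1.09, so it was about 9% too large.

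**4. If the factors act as continuous scores but are minimised as categories.** Splitting continuous scores at the median for minimisation weakens the balance. The ANOVA SE is then about 5% too large and its size about 4.3% at R2 = 0.20; at R2 = 0.10 the figures are about 2% and 4.8%.

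**5. Range.** Taking steps 3 and 4 together, the size of the unadjusted test is about 4–5% at R2 = 0.10 and about 3.5% at R2 = 0.20 (3.2% to 4.3% by scenario). Its SE is about 5–10% too large at R2 = 0.20.

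**The case against.** The strongest reply is that nothing false follows from the plan as written. The unadjusted contrast is not biased by balanced allocation, false positives are not inflated, and the sample size was computed for exactly this comparison and delivers its power. All of that stands. A reader might infer that the trial is underpowered or its tests invalid; the calculations show neither.

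A reader might also take 1.118 at R2 = 0.20 to mean an SE 12% too large, with a size of 2.8%. Those figures need perfect balance; realistic allocation and loss give the smaller ones above.

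R2 has no anchor in the protocol, and at R2 = 0 nothing is lost. Section 6.3.2 requires a Clinical Severity Rating of at least 4, which narrows the range of severity and probably its explanatory power. Nor does the background show that gender and disadvantage both predict cognition and behaviour. It ties disadvantage to cognition only, and gender to cognition and, tentatively, to behaviour. The passages quoted do not link either factor to attachment, and support for infant negative emotionality is weakest. These points limit the size of the concern but do not remove it.

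Last, section 9.2 calls treatment a factor and never says the only one, and the analysis plan, not available here, may add covariates. That is possible. But the protocol is not silent: it states a specific primary model without covariates, in the same paragraph that specifies ANCOVA for Hypothesis 2. The natural reading is an unadjusted model.

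**Conclusion.** The concern holds as a point about efficiency and mildly conservative inference, of moderate weight. The stated primary model does not match the allocation method. If the four factors explain 5% to 20% of outcome variance, leaving them out forgoes roughly 2 to 8 power points against the planned 80%, or about 3 to 6 against the simulated unadjusted power at R2 of 0.10 to 0.20. If they explain nothing, there is no material difference either way.

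The conclusion rests on three assumptions: the range for R2, a minimisation assignment probability of 0.8, and loss to follow-up unrelated to the factors. It also rests on reading section 9.2 as an unadjusted model, which the contrast with the ANCOVAs supports but does not prove.

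**What to change.** In section 9.2, for each continuous primary and secondary outcome at 24 months, replace the one-way ANOVA by a linear model with treatment arm plus child gender, socioeconomic status, infant negative emotionality and severity of postnatal depression. Report the adjusted mean difference with its 95% confidence interval as the primary result, and keep the unadjusted ANOVA as a sensitivity analysis. State how each factor is coded before the outcome data are examined by arm, so that covariates cannot be chosen afterwards. If the analysis plan already adjusts for these factors, bring the protocol wording into line with it.

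The cost is wording only. The factors must be known at randomisation for minimisation to work, so no new data are needed and the sample size need not change. With one parameter per factor, the residual degrees of freedom fall from 112 (2 × 57 − 2) to 108, which is negligible: at R2 = 0 the simulated power was 81.1% adjusted against 81.4% unadjusted.

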## 3. ABBREVIATIONS

AQS	Attachment Q-Sort
BSIDII	Bayley Scales of Infant Development II
BSIDIII	Bayley Scales of Infant Development III
CBCL	Caregivers Behaviours CheckList
CI	Chief Investigator
CTRG	Clinical Trials & Research Governance, University of Oxford
CBT	Cognitive Behaviour Therapy
CRB	Criminal Records Bureau
CSR	Clinical Severity Rating
DAS	Dyadic Adjustment Scale
ECBQ	Early Childhood Behavior Questionnaire
ECVT	Early Childhood Vigilance Task
EPDS	Edinburgh Postnatal Depression Scale
GP	General Practitioner
GCP	Good Clinical Practice
IBQ	(Rothbart) Infant Behaviour Questionnaire
IPPS	Infant-Parent Perinatal Service
IRAS	Integrated Research Application System
MDI	Bayley Mental Development Index
NRES	National Research Ethics Service
OBMH	Oxfordshire and Buckinghamshire Mental Healthcare NHS Trust
ОСТИМІ	Oxford Clinical Trials Unit for Mental Illness
OPT	Oxford Postnatal Treatment
PI	Principal Investigator
PIS	Participant/ Patient Information Sheet
PMR	Progressive Muscle Relaxation
PND	Postnatal Depression
PTSD	Post Traumatic Stress Disorder
R&D	NHS Trust R&D Department
REC	Research Ethics Committee
SAE	Serious Adverse Event
SCID	Structured Interview for DSM IV Diagnosis
SOP	Standard Operating Procedure

VFT	Video Feedback Therapy
IPA	Interpretative Phenomenological Analysis

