The 'Effortful Control' factor comprises 8 subscales. Of these, three ('Attentional Focusing', 'Attentional Shifting' and 'Inhibitory Control') are proposed for measuring attention of 2 year olds in the OPT study. Each of these subscales comprises 12 items. 'Attentional Focusing' measures the sustained duration of orienting on an object of attention and resisting distraction. 'Attentional Shifting' measures the ability to transfer attentional focus from one activity / task to another. 'Inhibitory Control' measures the capacity to stop, moderate or refrain from behaviour under instruction.

• Emotional Discrimination Task

Positive (happy), negative (sad) and neutral (calm) adult faces will be presented for 100 milliseconds each on a screen linked to an eyetracker to the children at 24 months. Attention-getters (cartoon images/movies) will be used in between each face of each battery of 12 face images as required to keep the child interested and attending to what is on the screen. Faces from the NimStim database will be used.

iii) *Maternal depression* will be measured at each time point using the EPDS and SCID. Depression at 24 months will be used as a secondary outcome. Although not an outcome variable, the fathers' depressive symptomatology will also be measured using the EPDS at each timepoint.

iv) Musical training and habits of the mothers will be measured at the final assessment via maternal report.

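### Maternal depression at 24 months is compared by a treatment-group ANOVA with no stated covariate, although baseline EPDS is collected: precision is lost, but the estimate is not biased

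*Protocol*

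**What the plan says.** Section 9.2 tests the child outcomes by ANOVA, with "each of the child outcomes measured at 24 months as the dependent variable and the treatment group as a betweengroup factor". It names no covariate for these models. It then adds: "The three secondary outcome variables will be analysed similarly".

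Section 6.2 numbers the 24-month secondary outcomes. The first three are emotion regulation, attention and maternal depression, and I read these as the three meant. Maternal depression "will be measured at each time point using the EPDS and SCID", and "Depression at 24 months will be used as a secondary outcome". The text does not say whether that means the EPDS score, the SCID diagnosis or both. Section 3 expands SCID as "Structured Interview for DSM IV Diagnosis".

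Three other statements bear on the point:

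- Section 6.4.3: "There will be three primary assessment points: (i) before treatment when the infant is 4½ - 9 months". A pre-treatment EPDS therefore exists.
- Section 6.1 lists the minimisation factors as "child gender, socioeconomic status, infant negative emotionality, and severity of PND".
- Section 9.2, for the parenting capacities: "ANCOVAs (co-varying for the 6m baseline measure) will be performed on each capacity".

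**The concern.** A model without a baseline term is understandable for the child outcomes. Among the assessments in section 6.4.3, the CBCL and the Bayley language scale first appear at 12 months, after the main therapy, and the full Bayley and the Attachment Q-Sort appear at 24 months. Maternal depression differs, because the same questionnaire is completed before treatment. The plan nevertheless carries the unadjusted model over to it, and adjusts for baseline only for the parenting capacities.

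Minimising on severity and then leaving severity out of the model has a further effect. Allocation removes some between-arm variation, but the standard error is computed as if that variation were still there.

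Both arms receive CBT, and the background argues that treating the mother's mood alone does not improve child outcome. A reader of the results will want to know how far the arms differed in maternal depression when interpreting any child effect. The protocol does not give the comparison that role explicitly, but a less precise comparison is less informative for that purpose.

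**Working it through.** **Inputs from section 9.1.** SD 10.9, difference 5.8, 5% significance (taken as two-sided, since sidedness is not stated), 80% power, 57 per group analysed, 20% loss, 72 per group randomised. The standardised detectable difference is 0.532 SD.

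**Reproducing the protocol's figures.** 5.8 / 10.9 = 0.532. Two-sample t-test power is 79.7% with 56 per group and 80.4% with 57, so 57 is right. 57 / 0.80 = 71.25, rounded up to 72. These figures concern the Bayley scale; the protocol gives no power calculation for maternal depression.

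**Gain from adjusting for baseline EPDS.** Let r be the within-arm correlation between baseline and 24-month EPDS. ANCOVA multiplies the residual variance by (1 − r²), so a difference d behaves like d / √(1 − r²). The protocol gives no value for r, so a range is assumed. I use d = 0.53 SD, borrowed from the Bayley calculation as an illustration only, and 57 per arm. The equivalent n is the number per arm that an unadjusted comparison would need for the same precision, 57 / (1 − r²).

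| r (assumed) | Variance removed, r² | 0.53 / √(1 − r²) | Power (t test) | Equivalent n per arm |
|---|---|---|---|---|
| none | 0% | 0.530 | 80% | 57 |
| 0.2 | 4% | 0.541 | 82% | 59.4 |
| 0.3 | 9% | 0.556 | 84% | 62.6 |
| 0.4 | 16% | 0.578 | 86% | 67.9 |
| 0.5 | 25% | 0.612 | 90% | 76.0 |

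**Effect of minimising on severity without adjusting for it.** Take the limiting case in which the arms are perfectly balanced on a severity measure that correlates r with the outcome. The true variance of the difference is then (1 − r²) times what the unadjusted test assumes, so the actual two-sided type I error is 2[1 − Φ(1.96 / √(1 − r²))]:

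- r = 0.3: 1.96 / √0.91 = 2.055, giving 4.0%.
- r = 0.5: 1.96 / √0.75 = 2.263, giving 2.4%.

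Real minimisation uses four factors and does not balance severity perfectly, so the true value lies between these figures and 5%. The error is on the conservative side.

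**SCID diagnosis under ANOVA.** With two arms, the group contrast from an ANOVA of a 0/1 variable is the difference in proportions. In a simulation of 200,000 trials with 57 per arm and equal true rates, the type I error was 5.0%, 5.3%, 5.1% and 4.9% at rates of 10%, 20%, 30% and 50%. The test keeps its size.

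**The case against.** The strongest reply is that nothing here is invalid. Randomisation keeps the unadjusted difference unbiased. A reader might infer that the comparison is left open to chance imbalance in baseline depression, but severity of PND is one of the four minimisation factors, so the design already limits that. This stands: the loss is in precision, with a test that errs on the cautious side.

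The gain may also be small. Entry requires a Clinical Severity Rating of at least 4, and on the GP-search route an EPDS of 13 or more, which narrows the baseline range. Baseline at 4½ to 9 months and follow-up at 24 months are 15 to 19½ months apart (24 − 9 and 24 − 4½), with CBT given in both arms. All of this points to a low r. At r = 0.2 power rises by less than 2 points. This stands as a limit on size, but not as a reason to discard a covariate already collected.

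The ANCOVA for parenting capacities answers a question about improvement, whereas the secondary outcomes are defined as 24-month levels. The contrast is therefore not a contradiction. It does show that baseline adjustment is already part of this plan.

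A reader might go further and infer that the plan has the wrong model, or no valid one, for the SCID diagnosis. The documents do not support that. They do not say that the diagnosis is the analysed variable, and present/absent coding is inferred from the instrument's name. If it is analysed, ANOVA on 0/1 data tests the risk difference at close to the nominal error rate. Nor does SCID offer a useful baseline of its own: eligibility requires diagnosed postnatal depression, so baseline diagnosis is nearly constant. The baseline argument applies to EPDS, and the modelling argument to SCID.

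Finally, calling ANOVA a treatment-group factor does not expressly forbid covariates, and the unseen SAP might add them. The protocol does, however, state a model and extend it to this outcome, and the point rests on that stated model.

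**Conclusion.** The point holds as an avoidable inefficiency in a stated model for one secondary outcome. The comparison of 24-month maternal depression is unbiased but less precise than the collected data allow, and it is conservative to the extent that minimisation on severity is effective.

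Its size depends on a correlation that the protocol does not give: from about 2 points of power at r = 0.2 to about 10 points at r = 0.5, for an illustrative 0.53 SD difference with 57 per arm. The lower part of that range is the more cautious expectation, given the restricted baseline severity.

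The SCID point is subsidiary and conditional. It concerns suitable modelling and reporting if a diagnosis is analysed, not validity. The primary child outcomes are unaffected.

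**What to change.** In section 9.2, separate maternal depression from the sentence that covers the three secondary outcomes, and state:

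- which 24-month depression variable or variables are analysed;
- that 24-month EPDS is analysed by ANCOVA with treatment group, baseline EPDS and the minimisation factors, reporting the adjusted mean difference with a 95% CI;
- that SCID diagnosis, if also analysed at 24 months, uses a binary model such as logistic regression adjusted for baseline severity (Clinical Severity Rating or EPDS), reporting the odds ratio and risk difference with 95% CIs.

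The linear model for the emotion-regulation and attention scores can stay. The cost is analysis wording only: no new data, visits or participants are needed, because the baseline values and minimisation factors are already collected.
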